3. STUDY OBJECTIVE AND TASKS

Primary objective of the study:

1. To confirm that the PK indices of the IMP BP-SCIG 20% are comparable with those of the BIOVEN product.
2. To confirm the adjustment factor for the dose of BP-SCIG 20% to ensure a steady-state area under the concentration-time curve (AUC) for the total IgG level, which is non-inferior to the values of BIOVEN, the drug of previous therapy.
3. To confirm that the threshold IgG levels (in administration of the IMP BP-SCIG 20% to patients with PID in a monthly dose of 0.4–0.8 g/kg, under a once a week regimen) are non-inferior compared to threshold IgG levels on previous therapy (in patients previously receiving human normal immunoglobulin products intravenously or another product of human normal immunoglobulin for subcutaneous administration), or those reported in the literature (in treatment-naïve patients).
4. Assessment of the efficacy, tolerability, safety, and pharmacokinetic parameters of BP-SCIG 20% in long-term use in patients with primary immunodeficiency with impaired antibody production.

Additional pharmacokinetic assessment objectives:

- To confirm the adjustment factor for the dose of BP-SCIG 20% to ensure a steady-state area under the concentration-time curve (AUC) for the total IgG level, which is non-inferior to the values of BIOVEN, the drug of previous therapy.
- To assess the variability of trough IgG levels in children and adolescents compared with adult patients.
- To determine the pharmacokinetic parameters (Cmax, AUC0-t, AUC0-∞, Tmax, t1/2, Kel, IR, Cl, AUCextrapol, Vd) for the IMP BP-SCIG 20% in 20 adult patients with PID, and compare them with the available published literature.
- To compare the results of pharmacokinetic data for patients who have not previously received human normal immunoglobulin products with published literature (descriptively).
- To compare the results of pharmacokinetic parameter study (Cmax, AUC0-t, AUC0-∞, Tmax, t1/2, Kel, IR, Cl, AUCextrapol, Vd) between the cohorts.

Safety and tolerability assessment tasks

- Conduct an interim safety assessment for the first 10 patients enrolled in the study who must be adults and must have received at least 4 IMP administrations.

Based on the results of such assessment (*interim report*), the possibility of enrolling patients younger than 18 years of age is determined;

- Assess the frequency of adverse events;
- Assess the incidence of adverse reactions to the IMP;

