4. STUDY DESIGN

4.1. Endpoints

Safety and tolerability endpoints

- Frequency of adverse events
- Incidence of adverse reactions to IMP
- Frequency of serious adverse reactions
- Emergence of treatment-emergent adverse events
- The frequency of treatment-emergent adverse events related to infusion rate
- The incidence of administration site reactions
- The frequency of clinically significant deviations in vital signs (blood pressure, body temperature, pulse rate and respiratory rate)
- The frequency of clinically significant deviations in laboratory findings (complete blood count, biochemical findings, markers of intravascular haemolysis, and coagulation parameters)

Safety data are also assessed separately in children and adolescents (after an interim assessment in adults) and compared with the adult data.

Primary pharmacokinetic endpoint:

Mean threshold (trough) plasma concentration of total IgG prior to the next administration of the product, when reaching steady state (after 4 months of treatment), assessed over 6 months.

Primary pharmacokinetic variable:

The monthly trough IgG levels, measured after 4 months of treatment with the IMP, prior to the next infusion, once every 4 weeks, over 6 months, did not fall below the trough levels of the previous therapy with SCIG or IVIG (BIOVEN).

Secondary pharmacokinetic endpoints

These endpoints are tested in the subgroup of subjects aged over 18 years who received treatment with BIOVEN prior to their enrolment in the study and, respectively, throughout the screening period:

- To confirm or calculate the IMP dose adjustment factor when converting from previous IVIG therapy with BIOVEN;

Tested in a subgroup of at least 20 adult patients with PID after approximately 4 months of treatment with the IMP BP-SCIG 20%:

- Area under the concentration-time curve (AUC)
- Maximum concentration (Cmax)
- Time to reach maximum concentration (Tmax)
- The threshold levels of total IgG during the dose titration phase (the dose-effect dependence)
- the *in vivo* elimination half-life
- the elimination constant
- serum clearance
- volume of distribution
- incremental recovery

Secondary endpoints are transformed into corresponding variables.

Primary efficacy endpoint:

Primary efficacy endpoint: The number of serious bacterial infections per subject per year (in order to achieve less than 1.0 infections/subject/year)

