 - Paediatric patients are required to undergo Visits 1 and 2 of the screening period. In the event of meeting the criterion “total serum IgG level ≥ 5 g/L – as confirmed by the results of at least two (2) measurements performed immediately prior to the subsequent administration of IVIG after signing the ICF”, the patient proceeds to treatment with the IMP BP-SCIG 20%, starting from Cycle 1. If the criterion is not met, then Visit 3 is performed.

- Adult patients are required to undergo Visits 1 and 2 of the screening period to determine whether they meet inclusion/non-inclusion criteria, and Visit 3 of the screening period to conduct a mandatory pharmacokinetic assessment of BIOVEN.
- For Cohort C, newly diagnosed (treatment-naïve) patients are required to undergo Visit 1 of the screening period; if meeting inclusion/non-inclusion criteria, the patient proceeds to treatment with the IMP BP-SCIG 20%, starting from Cycle 1.

Study phases. Treatment period.

The phase begins after the end of the screening period.

Cycles 1–13: These include on-site visits to the CTS: 4 visits in Cycle 1; all subsequent cycles: each first visit of the cycle (every 28 days \pm 3 days) and interim self-administrations of the product by patients in the home (every 7 days \pm 1 day) for 52 weeks. A total of 13 cycles that include 13 main on-site visits (1 visit to the CTS in each cycle), and 3 on-site visits for interim administration of the IMP. The period lasts 52 weeks.

Individualised dose titration is performed.

A loading dose of IMP may be required (at the Investigator's decision): at least 0.2–0.5 g/kg (1.0–2.5 mL/kg) of body weight. This dose is distributed across several days, with a maximum daily dose of 0.1 to 0.15 g/kg.

After achieving a steady-state level of IgG, maintenance doses are administered at repeated intervals (approximately once a week) to achieve a cumulative monthly dose of 0.4–0.8 g/kg. Each single dose must be administered to different anatomical locations. (see Section 6.1 of this Protocol).

Pharmacokinetic parameters of the IMP are assessed at Week 21 (see Table 4.2.2)

Cycle 1:

- Visit 4 (C1W1): **On-site visit** Week 1 – the first administration of the IMP BP-SCIG 20%;
- Interim administration 1(C1W2) on-site – Week 2, administration of the IMP;
- Interim administration 2(C1W3) on-site – Week 3, administration of the IMP;
- Interim administration 3(C1W4) on-site – Week 4, administration of the IMP.

Cycle 2:

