- Visit 5 (C2W5): **On-site visit** – Week 5 of IMP administration;
- Interim administration 1(C2W6) – Week 6, IMP administration in the home;
- Interim administration 2(C2W7) – Week 7, IMP administration in the home;
- Interim administration 3(C2W8) – Week 8, IMP administration in the home.

Cycle 3:

- Visit 6 (C3W9): **On-site visit** – Week 9 of IMP administration;
- Interim administration 1 (C3W10) – Week 10, IMP administration in the home;
- Interim administration 2(C3W11) – Week 11, IMP administration in the home;
- Interim administration 3(C3W12) – Week 12, IMP administration in the home.

Cycle 4:

- Visit 7 (C4W13): **On-site visit** – Week 13 of IMP administration;
- Interim administration 1(C4W14) – Week 14, IMP administration in the home;
- Interim administration 2(C4W15) – Week 15, IMP administration in the home;
- Interim administration 3(C4W16) – Week 16, IMP administration in the home.

Cycle 5:

- Visit 8 (C5W17): **On-site visit** – Week 17 of IMP administration;
- Interim administration 1(C5W18) – Week 18, IMP administration in the home;
- Interim administration 2(C5W19) – Week 19, IMP administration in the home;
- Interim administration 3(C5W20) – Week 20, IMP administration in the home.

Cycle 6:

- Visit 9 (C6W21): **On-site visit** – Week 21 of IMP administration; Start of additional visits for the assessment of pharmacokinetic parameters in adult patients. Assessment of PK parameters may require elective hospitalisation, which is not viewed as a SAR;
- Interim administration 1(C6W22) – Week 22, IMP administration in the home;
- Interim administration 2(C6W23) – Week 23, IMP administration in the home;
- Interim administration 3(C6W24) – Week 24, IMP administration in the home.

Cycle 7:

- Visit 10 (C7W25): **On-site visit** – Week 25 of IMP administration;
- Interim administration 1(C7W26) – Week 26, IMP administration in the home;
- Interim administration 2(C7W27) – Week 27, IMP administration in the home;
- Interim administration 3(C7W28) – Week 28, IMP administration in the home.

Cycle 8:

- Visit 11 (C8W29): **On-site visit** – Week 29 of IMP administration;
- Interim administration 1(C8W30) – Week 30, IMP administration in the home;
- Interim administration 2(C8W31) – Week 31, IMP administration in the home;
- Interim administration 3(C8W32) – Week 32, IMP administration in the home.

Cycle 9:

- Visit 12 (C9W33): **On-site visit** – Week 33 of IMP administration;

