6. TREATMENT OF SUBJECTS

6.1. Treatment regimen

The IMP shall be administered subcutaneously.

All patients will receive the investigational medicinal product BP-SCIG 20%, solution for subcutaneous administration manufactured by BIOPHARMA PLASMA LLC.

The IMP BP-SCIG 20% shall be administered at the frequency of once a week for 52 weeks, subcutaneously using a CRONO S-PID4 infusion pump.

The dosing regimen shall be designed to achieve a trough IgG level (at least 5–6 g/L), which will be measured before the next infusion.

Efforts must be taken to maintain serum IgG within the reference range for the corresponding age group of patients.

Individual dose selection and adjustment may be required for each patient, depending on the pharmacokinetic response (IgG level) and clinical response. Threshold levels must be assessed in combination with the incidence of infectious episodes. To reduce the risk of infection, it may be necessary to increase the dose and aim to achieve higher trough IgG levels.

A loading dose of IMP may be required (at the Investigator's decision): at least 0.2–0.5 g/kg (1.0–2.5 mL/kg) of body weight. This dose is distributed across several days, with a maximum daily dose of 0.1 to 0.15 g/kg.

After achieving a steady-state (minimal) level of IgG, maintenance doses are administered at repeated intervals (approximately once a week) to achieve a cumulative monthly dose of 0.4–0.8 g/kg. Each single dose must be administered to different anatomical locations.

Since the bioavailability of SCIGs is 30 % lower than that of IVIGs, partly due to binding to the extracellular matrix and cleavage by tissue enzymes (Wang et al. 2008; Berger et al. 2013), a dose adjustment factor of 1.37 will be used to convert the IVIG dose to the SCIG dose. This is based on historical data for bioequivalence evaluation of these administration routes (Wasserman et al. 2010, 2011; Berger et al. 2011) and meets the requirements of the US Food and Drug Administration (US FDA), according to which the SCIG doses must be adjusted to ensure an equivalent AUC for total IgG compared to previous IVIG therapy. Dose calculation for patients who received IVIG prior to the start of their participation in the study (John W Sleasman et al. 2019):

The initial dose of SCIG

$$\text{IgG} = \frac{\text{Previous IVIG dose (in grams)} \times 1.37}{\text{Number of weeks between IVIG administrations}}$$

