6.3.21 Safety of IMP use and Independent Safety Committee

Based on the publicly available data described in the literature, it has been established that SCIG products are generally well tolerated by patients, do not cause serious adverse reactions, and do not lead to clinically significant hazardous changes in the parameters of objective and laboratory examinations.

According to the available information on adverse reactions that may occur with the use of the IMP, the ICF for patients and parents in the CT protocol provides information about the use of the IMP (instruction on self-administration of the IMP) and a cautionary statement describing dangerous changes in the patient's health and the required actions by the patient/legally authorised representative or parents when such changes occur.

In addition, for the confirmation of such control, the patients (CT subjects) shall independently (through parents or a legally authorised representative) fill in the Patient's Diary, which is an important source document for the complete collection of data about any changes in the patient's health status and will allow independently analysing and appending information about adverse effects associated with the use of the IMP.

As for the physician's assessment of the subject's health status and making an appropriate decision regarding continuing/discontinuing the patient's participation in the CT, physicians will receive the Investigator's Brochure with the description of potential ARs and warnings, and, respectively, the algorithm of actions in the occurrence of an AE.

In addition, the Independent Safety Committee will conduct a safety assessment of the IMP after the first 10 adult patients receive at least 4 administrations of the IMP BP-SCIG 20%, or earlier, in the event of serious AEs, which may be potentially related to administration of the IMP and be defined as an AR.

After such an interim safety assessment in adult patients, the feasibility of including patients younger than 18 years is determined based on its results.

In addition, the Independent Safety Committee will conduct a safety analysis of the IMP for each age group of subjects after the patients receive their first 4 administrations of the IMP, prior to inclusion of a new age group of patients.

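### The safety review that opens paediatric enrolment, and each later age-group review, can be held a week before the first scheduled post-exposure safety laboratory tests, and nothing requires those results

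*Protocol*

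**What the plan says.** Section 6.3.21 sets the first review by a count of administrations: the committee "will conduct a safety assessment of the IMP after the first 10 adult patients receive at least 4 administrations of the IMP BP-SCIG 20" per cent, or earlier if potentially related serious adverse events occur. Section 3 uses the same count, saying that the first ten patients "must be adults and must have received at least 4 IMP administrations". Sections 4.2 and 5 repeat it. The decision that hangs on the review is stated plainly: "After such an interim safety assessment in adult patients, the feasibility of including patients younger than 18 years is determined based on its results".

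Section 6.3.21 then uses the same count for each age group. The committee analyses safety "after the patients receive their first 4 administrations of the IMP, prior to inclusion of a new age group of patients". It does not say how many patients per group this covers.

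Section 4.2 places the fourth infusion at "Interim administration 3(C1W4) on-site – Week 4, administration of the IMP". The next on-site visit is Visit 5, "Week 5 of IMP administration". Table 4.2.1 marks blood count, chemistry, Coombs' test and haptoglobin as mandatory at Visit 1, C1W1 and C2W5, with nothing for Weeks 2–4. The coagulation panel is mandatory at Visit 1, optional at C1W1, and next mandatory at C2W5.

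Section 4.1 lists among the safety endpoints "The frequency of clinically significant deviations in laboratory findings (complete blood count, biochemical findings, markers of intravascular haemolysis, and coagulation parameters").

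**The concern.** The trigger counts infusions, while the laboratory schedule runs by visit, and the two are one week apart in the unhelpful order. The protocol reports only non-clinical studies of this product and otherwise relies on literature for other subcutaneous immunoglobulins. The first ten adults therefore supply the product-specific human safety evidence on which children are admitted. If the review is held as soon as its condition is met, part of that evidence has not yet been collected, and the missing part includes the haemolysis and clotting tests that the protocol itself treats as safety outcomes. How much is missing depends on the pace of enrolment, which the protocol does not control for this purpose.

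**Working it through.** **1. Which tests are drawn when.** Section 6.3.13 gives tube volumes (chemistry with IgG 5.5 mL, haptoglobin 3.5, Coombs' 2, blood count 2, glucose 2, coagulation 3, glycated haemoglobin 4) and a total per visit. Adding the tubes that Table 4.2.1 marks as mandatory reproduces the stated totals:

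- Visit 1: 5.5 + 3.5 + 2 + 2 + 2 + 3 + 4 = 22 mL (stated 22)
- Visit 4 (C1W1): 5.5 + 3.5 + 2 + 2 + 2 = 15 mL (stated 15)
- Visit 5 (C2W5): 15 + 3 = 18 mL (stated 18)

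No volume is listed between Visits 4 and 5, and the same section says that blood is taken once per 4-week period. The table and the volume list agree that there is no scheduled draw in Weeks 2–4.

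**2. Whether C1W1 counts as post-exposure.** The IgG sample at C1W1 is pre-administration and shares the chemistry tube. The C1W1 draw is therefore in effect a baseline, although the protocol does not state the timing test by test.

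**3. Dates.**

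- Fourth weekly infusion: Day 1 + 3 × 7 = Day 22
- Visit 5: Day 1 + 4 × 7 = Day 29
- Nominal gap: 29 − 22 = 7 days
- With the windows in section 4.5 (±1 day for infusions, ±3 days for visits), applied to the nominal days: from 26 − 23 = 3 to 32 − 21 = 11 days. The draw still comes after the trigger.

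**4. How many of the ten adults have results at the earliest trigger.** Let s be each adult's start day and s10 that of the last to start. The trigger falls at s10 + 21. An adult has had the Week 5 draw by then if s + 28 ≤ s10 + 21, that is, if s10 − s ≥ 7 days. With laboratory turnaround L, the condition is s10 − s ≥ 7 + L. The tenth adult never meets it. For evenly spaced starts (an assumption):

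| Span of the ten starts (days) | Week 5 draw done | Result available, L = 7 days |
|---|---|---|
| 0–6 | 0 of 10 | 0 of 10 |
| 7 | 1 | 0 |
| 14 | 5 | 1 |
| 28 | 7 | 5 |
| 42 | 8 | 7 |
| 56 | 8 | 7 |
| 67 | 9 | 8 |

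**5. Which span the protocol implies.** Section 4.5 gives 28 months in total and up to 62 weeks per patient; section 4.2 gives 56 patients. At 30.44 days per month, 28 × 30.44 − 62 × 7 = 852.3 − 434 = 418.3 days for entry. That is 418.3 / 56 = 7.47 days per patient, so the first ten starts span 9 × 7.47 = 67 days. The last row of the table applies: about 8 to 9 of 10.

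**6. Age groups.** The planned minimums in section 4.2 are 2 patients (0 to ≤2 years) and 4 patients (>2 to ≤6 years). The condition in step 4 applies unchanged. If all patients in such a group start within less than 7 days of each other, none has a scheduled post-exposure result at the earliest trigger.

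**The case against.** The strongest reply is that four administrations is a floor and not a data cut. The wording allows a later review, an interim report has to be written and read, and nothing excludes results that arrive meanwhile. A gap of 7 days could close on its own. That is fair, but it describes what may happen; the protocol does not require it.

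Second, a reader might infer that the committee would have no post-exposure laboratory results at all. The documents do not support this for the adult review. It needs all ten adults to start within about a week of each other, or about two weeks with a 7-day turnaround. Cohorts also have screening periods of different length, which tends to spread the starts.

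Third, a reader might infer that the count could be met within days, because a loading dose is split: "This dose is distributed across several days, with a maximum daily dose of 0.1 to 0.15 g/kg". This does not stand. Sections 4.2 and 6.1 treat the first four administrations as the weekly on-site training infusions, and the loading dose is a single optional dose given in portions.

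Fourth, the early infusions are supervised on site, and extra tests are permitted. This stands in part. The review would not rest on adverse-event reports alone, but the footnoted Coombs' and haptoglobin tests depend on haemolysis already being seen in laboratory results, and an unscheduled visit needs a reason.

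Fifth, children already on immunoglobulin need two screening visits at least 21 days apart. If they are screened only after the review, the tenth adult's Week 5 draw would precede their first dose. Treatment-naive children need only Visit 1, however, and nothing asks the committee to look again.

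Finally, section 4.1 lists endpoints for the whole study and does not define the content of the interim report. That is correct, and it is part of the point: the content is left open.

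**Conclusion.** The point holds in a limited form. Every review that opens enrolment to children or to a new age group can be held on nominal Day 22 of the last patient counted, 7 days before that patient's first scheduled post-exposure safety bloods. In the adult review at least one of the ten, the tenth, lacks such a result at the earliest trigger. Between 0 and 9 have had the draw, and about 8 to 9 if entry is even over the timeline in section 4.5. The exposure is greatest in the smallest paediatric groups, where near-simultaneous starts are plausible and none may have results.

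This rests on weekly dosing, on the C1W1 draw being a baseline, and, for the 8-to-9 figure only, on evenly spaced starts. Faster early enrolment would lower that figure. No efficacy or pharmacokinetic analysis is affected. It is an inexpensive improvement to a safety rule and does not invalidate the design.

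**What to change.** In sections 3, 4.2, 5 and 6.3.21, replace the count of administrations as the trigger. For the adult review: the first 10 treated adults have completed Visit 5 (C2W5) and its laboratory results are available to the Independent Safety Committee. For each age-group review: the same condition, applied to the patients of that group. Keep the existing provision for an earlier review if potentially related serious adverse events occur.

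The tests, the visit and the 18 mL draw are already scheduled, so nothing is added for patients or sites. The cost is a change of wording in four sections and a delay of about 7 days plus laboratory turnaround at each review.

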6.3.22 Contraception and pregnancy

Before the onset of participation in the study, male and female subjects of reproductive potential will be informed about the importance of using contraception throughout the study period and for 30 days after its completion. Study subjects with intact reproductive potential must use effective methods of barrier contraception. The objective of using barrier contraception is to prevent the occurrence of sexually transmitted diseases, including HIV, HBV, and HCV.

According to the "Recommendations related to contraception and pregnancy testing in clinical trials", Version 1.2, highly effective birth control methods are defined as methods that, when used consistently and correctly, can achieve a failure rate of less than 1 % per year. Such methods include:

- combined (oestrogen–progestogen) contraception associated with inhibition of ovulation;
- oral, intravaginal, or transdermal hormonal contraception;
- progestogen-only hormonal contraception associated with inhibition of ovulation;
- oral/injectable/implanted contraception;
- intrauterine device (IUD);
- intrauterine hormone-releasing system (IUS);
- bilateral tubal occlusion;
- partner's vasectomy;
- sexual abstinence.

The acceptable birth control methods, with an annual failure rate over 1 %, include the following:

- progestogen-only oral hormonal contraception where inhibition of ovulation is not the principal mode of action;
- a male or female condom with or without spermicide;
- a cervical cap, diaphragm, or spermicide sponge.

The combinations of a male condom with a cervical cap, diaphragm, or spermicide sponge (double-barrier methods) are also considered acceptable, but not highly effective birth control methods.

Participation in the study is also available for women who are not using acceptable methods of contraception if they are recognised to have no childbearing potential, i.e.:

- female subjects who have undergone a hysterectomy (removal of the uterus) or tubal ligation;
- female subjects with a clinical diagnosis of infertility;
- female subjects who are in the postmenopausal period for more than 1 year (absence of menstruation for at least 12 months);
- female subjects who have not had a menarche.

